 - ii. **Exploratory hypothesis 1b**: Family member need burden will be higher based on patient trigger status (present vs. absent), even after adjustment for sociodemographic and patient characteristics.
- 2. **Specific Aim 2**: Develop a need-targeted, ICU-based palliative care collaborative care delivery model.
 - a. Goal 2a: Develop a provisional collaborative ICU-based palliative care model based on Aim 1's need typologies, clinician skill in addressing needs, clinician attitudes, and published guidelines. The algorithm-based model will display recommendations for addressing needs (ICU team or ICU team plus specialist palliative care) on a mobile app viewable on any electronic device.
 - b. Goal 2b: Test the care model's acceptability among clinicians, using qualitative analysis of focus groups and quantitative satisfaction metrics. Model improvements will be made in an iterative process.
- 3. Aim 3 (exploratory): Using mixed methods (semi-structured interviews and quantitative process measures), characterize the impact of ICUconnect across a variety of family-and patient-implementation contexts, with a goal of understanding intervention mechanisms and family members' unique experiences of having a loved one in an ICU—before or during COVID.
 - 1. Approach & goal: We will integrate content analysis via a semi-structured interview with previously enrolled family members as well as quantitative family, patient, and care process outcomes. The content analysis will provide insight into ICUconnect' mechanisms of action, relate outcomes to unique case contexts, and help lead to future intervention optimization, replicability, and scalability. It is hoped that this aim may also provide meaningful information to field regarding the effects of COVID-19 on family members who have had a loved one in an ICU setting.

[figure not shown]
Background & Significance

• Should support the scientific aims of the research

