Assuming that a participant receives a NEST score of \geq 15, regardless of clinician randomization, the participant will continue with the following study procedures:

- Survey 2 (T2) to be completed within 3 days (0/+1 day) of T1 completion.
- Survey 3 (T3) to be completed within 7 days (0/+3 days) of T1 completion
- Survey 4 (T4) to be completed within 3 months (90 days, 0/+3 days) of T1 completion.

Should a participant receive a NEST score of \geq 15 and be randomized to an intervention clinician, the participant will be contacted by the intervention clinician have a family meeting. Family meetings are to occur after the completion of T1 but prior to the completion of T2. Given the short timeframe between T1 and T2, the clinician can conduct the family meeting in a variety of settings: in the ICU at bedside, in a private conference room and/or location within the waiting room (at the choice of the participant), and/or over the phone.

In conjunction with Aims 2 and 3 of the RCT, the study team will simultaneously enroll patient/family dyads into the ancillary study. The ancillary study will include a total of 250 enrolled patient/family dyads. Eligible participants will be approached for consent at the time of the ICU admission. Participants enrolled into the ancillary study will be those participants whose current attending clinician is not enrolled in the RCT and/or their identified primary race and ethnicity is something other than White or African American /Black and Non-Hispanic. Participants enrolled in the ancillary study, like the RCT, must meet study eligibility criteria.

Participants enrolled into the ancillary study will complete an ICUconnect profile and then be asked to complete the following surveys:

- Survey 1 (T1) to be completed within 24 hours of consent.
- Survey 2 (T2) to be completed within 3 days (0/+1 day) of T1 completion.
- Survey 3 (T3) to be completed within 7 days (0/+3 days) of T1 completion
- Survey 4 (T4) to be completed within 3 months (90 days, 0/+3 days) of T1 completion.

Given that the targeted patient population involves individuals who are seriously ill and/or injured, the study team expects that there is a high likelihood that death could occur while the patient/family dyad's participation is ongoing. Should a patient pass away while study participation is ongoing, the following will occur:

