- If the patient passes after the completion of T1 but prior to the completion of T2, the patient/family dyad will be withdrawn from the study.
- If the patient passes after the completion of T1 and T2 but prior to T3 completion, the patient /family dyad will remain eligible to continue study participation; however, the study team will be mindful and sensitive regarding approach and may skip T3. It is not considered a deviation if the family completes T3 prior to the study team enabling the "skip" option within ICUconnect.

• If the patient passes after the completion of T1, T2, and T3 but prior to completion of T4, the study team may wait 1 month before asking the family to complete the fourth and final study survey. It is not considered a deviation if the family completes T4 1 month late.

In regards to survey completion, it is understood, given the nature of the study design (self-directed participant survey completion), that surveys may not be completed in the specified protocol windows. The study team will provide participant education at the time of consent regarding the importance of completing surveys in a timely manner. In addition, the study team will follow-up with participants (patient /family dyads and clinicians) via phone, email, and in-person to complete study surveys and/or family meetings, as applicable.

The study consists of the following statuses for patient/family dyads:

- Consented: an individual(s) who meets all eligibility criteria and has voluntarily agreed to participate in the study (RCT or ancillary).
- Enrolled: an individual whom, after consent is obtained, completes the first survey.
 - Nte: if a participant is enrolled in the RCT study and receives a NEST score of < 15, he/she
 is deemed a screen failure and is therefore no longer enrolled. If a participant is enrolled in
 the ancillary study, he/she does not need to meet a NEST threshold for enrollment.
- Screen Fail: any participant who is enrolled into the RCT and receives a score of < 15.
- Withdrawn by PI: any participant who does not comply with study specific requirements (i.e. such as timely completion of study surveys, specifically T1 and/or T2) or is found to be by the principal investigator no longer appropriate for this study due to current state of being (physical, mental and /or emotional).
- Withdrawn by Self: voluntary withdraw of participant from study for any reason.
- Completed: any participant (RCT or ancillary) who completes 75% of study visits.

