 - b. If a patient is intubated on the day of eligibility but then subsequently extubated the same day, the patient remains eligible for the study as long as consent and T1 are completed within 8 hours of extubation.
- 3. Death must not be imminent (< 24 hours)

Inclusion Criteria (Family Members, Pre-Consent)

- 1. One family member per patient is eligible.
- 2. The family member must be \geq 18 years old.
- 3. The family member must be self-described as the individual (related or unrelated) who provides the most support and with whom the patient has a significant relationship.

Inclusion Criteria (Clinician, Pre-Consent)

1. Patients' bedside ICU attending physicians on the day of family consent are eligible.

Exclusion Criteria (Patients, Pre-Consent)

- 1. Patients who are admitted to an ICU at the index hospital >14 days will be ineligible for participation.
- 2. Patients who are on comfort care or are planned to undergo withdrawal of treatment within the following 48 hours of enrollment will be excluded.
- Prisoners
- 4. Patients who have no known family or surrogate.
- 5. Patients who are transferred to a non-study ICU or non-study clinician will be excluded if they are enrolled into the RCT only.

Exclusion Criteria (Family Members, Pre-Consent)

- 1. Family members will be excluded if they lack English fluency or have other limiting factors that inhibit their ability to use the app (e.g. literacy, blindness, etc).
- 2. Family members will be excluded if they are not directly involved in decision making, are unreachable or unavailable.
- 3. Family members will be excluded if they are <18 years of age.
- 4. Family members will be excluded if they are unable to consent (e.g., dementia, cognitive impairment).
- 5. Prisoners.
- 6. For the RCT only: family members who self-identify as Hispanic and/or self-identify most with a racial group other than White or Black will be excluded.
 - a. Ethnic and racial exclusions do not apply to the ancillary study.

Exclusion Criteria (Patient/Family Dyad Post-Consent)

- 1. Patient dies before T2 is completed.
- 2. Family members will be excluded from the RCT, but not the ancillary study, who have a very low need burden (NEST < 15) after the completion of T1.
- 3. For the primary RCT, participants are also excluded if the randomized physician leaves ICU service or is replaced by a non-participating ICU physician < 2 calendar days after family completes T1.

For Aim 4 RCT (or Aim 3 Ancillary Study) Only:

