Aim 1: The primary goal of the cohort study (Aim 1) is to derive 3-5 clinically rational palliative care need typologies, or subgroups with a phenotypic homogeneity of need severity and type, to inform Aim 2's derivation of a care delivery model. These analyses will be conducted within the framework of latent class analysis (LCA), a statistical methodology that uses contingency table analyses to discern response patterns across a series of categorical variables. LCA will be applied to the dichotomized (high vs. low need) NEST item scores to identify latent (i.e., unobservable) subgroups of need classes within family members at T1 via maximum likelihood estimation (SAS PROC LCA). Study investigators will iteratively develop more fully formed needs typologies resulting from these analyses in a series of face-to-face investigator meetings using a decision-rule process. We will provisionally classify need typologies as 'simpler' (ICU team can address) or 'complex' (specialist care advised).

Exploratory hypotheses: Hypothesis 1aexplores the potential value of a novel intervention target—'unmet needs,' defined as a NEST summary score at T2 that is greater than T1 for those completing both interviews. This hypothesis will be confirmed if the unmet needs coefficient is statistically significant after regressing PHQ-9 scores at T4. Hypothesis 1bwill tested via a multivariable regression model with NEST summary score as the outcome and trigger status (present / absent) as the coefficient of interest, adjusted for sociodemographic and clinical variables. We anticipate < 10% missing data between T1 and T2.

Aim 2: This Aim's primary goal is to develop a provisional collaborative model of ICU-based palliative care using a mixed methods approach in which qualitative focus group data from family members, self-reported skills confidence data from clinicians, and expert guidelines will be integrated with Aim 1's need typologies. Step 1: validate needs typologies. 3 focus group interviews with family members purposively sampled from each of Aim 1's needs typologies subgroups will be conducted to validate the needs typologies in participants' own voices, verify the complexity of needs, and allow us to look beyond socioemographic variables for other common factors shared by subgroup members. Transcripts will be

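### The rule that excludes dyads when the patient dies before T2 also covers the ancillary cohort, so its T1-only need typologies would rest on a sample selected by a later event

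*Protocol*

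**What the plan says.** In the protocol's Selection of Subjects, the post-consent exclusions for dyads have three items. The first is "Patient dies before T2 is completed", with no mention of either study. The second begins "Family members will be excluded from the RCT, but not the ancillary study, who have a very low need burden" and the third begins "For the primary RCT, participants are also excluded if the randomized physician leaves ICU service"; both are expressly confined to the RCT.

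Design & Procedures repeats the first rule. When death follows T1 but comes "prior to the completion of T2, the patient/family dyad will be withdrawn from the study". This text comes directly after the ancillary survey schedule and again names no study. The same section warns that "there is a high likelihood that death could occur while the patient/family dyad's participation is ongoing". The interval at issue is short on paper: "Survey 2 (T2) to be completed within 3 days (0/+1 day) of T1 completion". But the section also expects surveys to be returned late and does not count that as a deviation.

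The ancillary statistical methods make the derivation of need typologies the primary goal of the cohort. The latent class model is fitted to dichotomised NEST items "to identify latent (i.e., unobservable) subgroups of need classes within family members at T1". The SAP does not cover the ancillary analyses.

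**The concern.** A family that has completed T1 has supplied everything the latent class model uses. Excluding it afterwards because the patient died before T2 makes membership of the analysis set depend on an event that came after the measurement. The typologies and their relative sizes would then describe families whose patient survived to T2 completion, not the families who were assessed at T1.

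The cut-off is completion of T2, not a fixed day. For a family that answers late, the patient must survive longer for the family to stay in. The selection therefore depends partly on how quickly the family responds.

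Hypothesis 1b, which compares need burden by trigger status, may be affected in the same way. That depends on the NEST time point it uses, which the protocol does not give.

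**Working it through.** **Does the rule reach the ancillary cohort?**

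- Items 2 and 3 of the post-consent list carry an RCT limit and item 1 does not. The pre-consent lists show the same habit: transfer to a non-study ICU or clinician, and the race and ethnicity criterion, are marked as RCT-only. The authors limited criteria to the RCT where they meant to.
- The withdrawal rule in Design & Procedures is also unrestricted.
- An RCT-only reading would not remove the issue on the Research Abstract's count, where 130 of the 200 ancillary family members are RCT controls (130/200 = 65%). Design & Procedures describes the ancillary cohort differently, so this is supporting evidence only.

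**Does exclusion remove the T1 answers?** The protocol points both ways.

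- The status list in Design & Procedures treats a participant as enrolled once the first survey is complete.
- The inclusion criterion for RCT Aim 4 (ancillary Aim 3) takes enrolled to mean that the pre-consent and post-consent criteria were all met.
- Subject Recruitment and Compensation counts the 250 ancillary dyads as those that satisfy all criteria.
- Nothing says that T1 answers of dyads withdrawn for death are kept. The statement about using all available data and the missing-data paragraph belong to the RCT aims.

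Read literally, an unmet eligibility criterion takes the dyad out of the cohort.

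**Is there a figure in the plan to reproduce?** None bears on this point. The ancillary sample size of 184 (5-point difference, SD 12, 5% type I error, 80% power) does reproduce: a two-sided two-sample t-test needs 91.4 per group, so 92 per group and 184 in all. It concerns met versus unmet needs. The latent class power for 200 cannot be checked, because no class sizes or item probabilities are given.

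**How far could a class share move?** The inputs below are assumptions, except the cohort of 200, which comes from the ancillary power section.

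- f = share of T1 completers whose patient dies before T2: 5% or 10%
- true high-need class: 20%, that is 40 of 200
- s = share of early-death families in that class: 20%, 40% or 60%

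Share after exclusion = (40 − s × 200f) / (200 − 200f)

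| s | f = 5% (10 excluded) | f = 10% (20 excluded) |
|---|---|---|
| 20% | (40 − 2)/190 = 20.0% | (40 − 4)/180 = 20.0% |
| 40% | (40 − 4)/190 = 18.9% | (40 − 8)/180 = 17.8% |
| 60% | (40 − 6)/190 = 17.9% | (40 − 12)/180 = 15.6% |

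If early-death families were less often high-need, the sign would reverse. At s = 10% the shares are (40 − 1)/190 = 20.5% and (40 − 2)/180 = 21.1%.

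**Does replacing excluded dyads help?** It restores the number but not the mix. To keep 200 after exclusion, 200/0.95 gives 211 T1 completers (11 discarded) and 200/0.90 gives 223 (23 discarded). The replacements who stay in are also families of patients who survived to T2, so the expected shares in the table do not change.

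**The case against.** The strongest reply is that withdrawal does not mean deletion. The protocol never says that T1 answers are discarded. It calls T1 completers enrolled, limits only Hypothesis 1a to families with both interviews, and fits the latent class model to family members at T1. An analyst could fairly read this as keeping every T1 questionnaire. The consent pages, which might settle use of data after withdrawal, are not in the text available. This stands as far as it goes: exclusion from the analysis follows from the criterion's wording, and deletion is not stated. But one reading keeps these families and the other drops them, so the protocol still has to say which applies.

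A second reply is that T2 matters to the ancillary study. Aim 1 covers how needs evolve, and the clinician discussions are expected to consider change from T1 to T2. That justifies requiring T2 for those analyses, but not for the typologies.

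A third reply is that class shares are not the typologies. Investigators develop the typologies by a decision process and then judge whether the ICU team can meet the need or specialist care is advised. Focus groups, clinician confidence and guidelines also shape the care model. This stands: a shifted share does not show that any class would vanish or be classified differently.

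Finally, patients whose death is imminent, who are on comfort care or who have withdrawal of treatment planned are excluded before consent. The families lost here are those of the patients who die earliest among those eligible, not of all the sickest patients in the ICU.

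**Conclusion.** The point holds as a design choice worth correcting. The exclusion, as written, covers the ancillary cohort and conditions an analysis of T1 answers on survival to T2 completion. In the illustration, a true 20% class is estimated at 20% if early-death families have the same needs, and at 18.9% to 15.6% if 40-60% of them are high-need. Those figures rest on assumed death rates of 5-10% and an assumed class size. The documents supply no early-death rate and no relation between early death and family need, so neither the size nor the direction of any bias can be derived from them.

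A reader might infer more, and the documents do not support it:

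- **Lost power.** Subtracting 10-20 families from 200 ignores the plan to consent about 300 dyads so that 250 satisfy all criteria. Over-recruitment can replace the excluded dyads.
- **A diluted trigger effect.** This would require early death to be commoner when triggers are present and also linked to higher need. Neither is documented, Hypothesis 1b is exploratory, and its NEST time point is not stated.
- **A care model that fails at ICU entry, or for those who most need specialist referral.** The protocol does not describe triage at ICU entry. Patients need at least 24 hours of ventilation and may have been in the ICU for up to 14 days. It also does not say for whom referral matters most.

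**What to change.** Make three small wording changes in the protocol.

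1. In the post-consent exclusion list and in the Design & Procedures text on death, state that death before T2 ends further follow-up of the dyad but does not remove T1 data from the ancillary study.
2. In the ancillary statistical methods, state that every ancillary family completing T1 enters the T1 latent class analysis, whatever happens to the patient afterwards.
3. In the same place, give the NEST time point for Hypothesis 1b. If it is T1, apply the same inclusion rule.

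Analyses that need T2 or T4 (Hypothesis 1a and change over time) stay restricted to families with those surveys. The sponsor should confirm that consent allows use of data already collected from withdrawn dyads. Subject to that, the cost is a few sentences: no extra enrolment, no new data collection and no added contact with bereaved families.
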